Participants may be unblinded after BICR-verified disease recurrence at the investigator discretion upon Sponsor consultation only if this information is required to guide future treatment decisions.

If participant is unblinded, the circumstances around the unblinding (eg, date and reason) must be documented promptly. Only the principal investigator or delegate and the respective subject's code should be unblinded. Sponsor personnel directly associated with the conduct of the study should not be unblinded.

Follow-up visits and imaging schedules will be scheduled per the SoA (Section 1.3).

The primary endpoints of the study are RFS by BICR and OS. This study will also examine the safety and tolerability of pembrolizumab versus placebo administered Q3W for 17 cycles and PROs as secondary endpoints. Safety evaluations will include AE monitoring, physical examinations, clinical laboratory parameters (hematology and chemistry), vital signs, and assessment of Eastern Cooperative Oncology Group (ECOG) performance status (see Appendix 9). AEs will be monitored throughout the study and graded in severity according to the guidelines outlined in the National Cancer Institute (NCI) Common Terminology Criteria for Adverse Events (CTCAE) Version 4.0.

Patient-reported outcomes (PROs) are secondary endpoints evaluating any clinically relevant differences between the two treatment arms in global QoL.

This study will be conducted in conformance with Good Clinical Practices.

CCI

Results of the interim analyses will be reviewed by an external Data Monitoring Committee (eDMC), which will make recommendations to the Sponsor to continue, modify, or end the study according to the plan described briefly in Section 4.4.1 and in detail in Section 9.

The study will be considered a success if superiority in RFS is established.

NOTE: Country-specific protocol operational items are described in Appendix 7.

Specific procedures to be performed during the study, as well as their prescribed times and associated visit windows, are outlined in the SoA in Section 1.3. Details of each procedure are provided in Section 8.

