8.1.10 Participant Blinding/Unblinding

STUDY INTERVENTION IDENTIFICATION INFORMATION IS TO BE UNMASKED ONLY IF NECESSARY FOR THE WELFARE OF THE PARTICIPANT. EVERY EFFORT SHOULD BE MADE NOT TO UNBLIND.

For emergency situations where the investigator or medically qualified designee (consistent with local requirements) needs to identify the intervention used by a participant and/or the dosage administered, he/she will contact the emergency unblinding call center and make a request for emergency unblinding. As requested by the investigator or medically qualified designee, the emergency unblinding call center will provide the information to him/her promptly and report unblinding to the Sponsor. Prior to contacting the emergency unblinding call center to request unblinding of a participant's intervention assignment, the investigator who is a qualified physician should make reasonable attempts to enter the toxicity grade of the AEs observed, the relation to study intervention, the reason thereof, etc., in the medical chart. If it is not possible to record this assessment in the chart prior to the unblinding, the unblinding should not be delayed.

In the event that unblinding has occurred, the circumstances around the unblinding (eg, date, reason, and person performing the unblinding) must be documented promptly, and the Sponsor Clinical Director notified as soon as possible.

Once an emergency unblinding that is part of the study design has taken place, the investigator, site personnel, and Sponsor personnel may be unblinded so that the appropriate follow-up medical care can be provided to the participant.

Participants whose treatment assignment has been unblinded by the investigator or medically qualified designee and/or nonstudy treating physician must be discontinued from study intervention, but should continue to be monitored in the study.

Additionally, the investigator or medically qualified designee must go into the IRT system and perform the unblind in the IRT system to update drug disposition. In the event that the emergency unblinding call center is not available for a given site in this study, the IRT system should be used for emergency unblinding in the event that this is required for participant safety.

At the end of the study, random code/disclosure envelopes or lists and unblinding logs are to be returned to the Sponsor or designee.

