8.2.2 Patient-reported Outcomes

The EQ-5D-5L and EORTC QLQ-C30, and EORTC QLQ-HCC18 questionnaires will be administered by trained site personnel and completed by participants in the following order: EQ-5D-5L first, then EORTC QLQ-C30, then EORTC QLQ-HCC18. The questionnaires should be administered prior to dosing on Day 1 of each cycle from Cycle 1-10 both inclusive, then on Day 1 of Cycle 12, 14, 16, at EOT, and at the 30-day Safety Follow-up Visit. For participants who discontinue from study intervention prior to Cycle 17, PROs will be collected Q12W from the EOT Visit during the remainder of Year 1. After Year 1, PROs are to be performed Q24W to align with imaging visits. After Year 2, PROs are to be performed Q24W to align with imaging visits, up to and including Week 216. PROs are collected again at Week 228, and Week 252 PROs should be collected up to and including Year 5 (Week 252).

It is best practice and strongly recommended that patient-reported outcomes (PROs) are administered to randomized participants prior to drug administration, AE evaluation, and disease status notification. If the participant does not complete the PROs at a scheduled time point, the MISS_MODE form must be completed to capture the reason the assessment was not performed.

NOTE: For some sites, the translated EORTC QLQ-C30 and/or EORTC QLQ-HCC18 might become available after study startup and should be administered to participants at their time of enrollment; for some sites, the EORTC QLQ-C30 and/or EORTC QLQ-HCC18 translation might not be available for the entire duration of the study.

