All AEs meeting serious criteria, from the time of intervention allocation/randomization through 90 days following cessation of study intervention or 30 days following cessation of study intervention if the participant initiates new anticancer therapy, whichever is earlier, must be reported by the investigator.

All pregnancies and exposure during breastfeeding, from the time of intervention allocation/randomization through 120 days following cessation of study intervention, or 30 days following cessation of study intervention if the participant initiates new anticancer therapy must be reported by the investigator.

Additionally, any SAE brought to the attention of an investigator at any time outside of the time period specified above must be reported immediately to the Sponsor if the event is considered related to study intervention.

Investigators are not obligated to actively seek AEs or SAEs or other reportable safety events in former study participants. However, if the investigator learns of any SAE, including a death, at any time after a participant has been discharged from the study, and the investigator considers the event to be reasonably related to the study intervention or study participation, the investigator must promptly notify the Sponsor.

All initial and follow-up AEs, SAEs, and other reportable safety events will be recorded and reported to the Sponsor or designee within the time frames as indicated in [Table 6](#).

Table 6 Reporting Time Periods and Time Frames for Adverse Events and Other Reportable Safety Events

Type of Event	Reporting Time Period: Consent to Randomization/ Allocation	Reporting Time Period: Randomization/ Allocation through Protocol-specified Follow-up Period	Reporting Time Period: After the Protocol- specified Follow-up Period	Time Frame to Report Event and Follow-up Information to Sponsor:
Nonserious Adverse Event (NSAE)	Report if: - due to protocol-specified intervention - causes exclusion - participant is receiving placebo run-in or other run-in treatment	Report all	Not required	Per data entry guidelines
Serious Adverse Event (SAE) including Cancer and Overdose	Report if: - due to protocol-specified intervention - causes exclusion - participant is receiving placebo run-in or other run-in treatment	Report all	Report if: - drug/vaccine related. (Follow ongoing to outcome)	Within 24 hours of learning of event

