9.6.2.1 Overall Safety Assessment

The overall safety evaluation will include a summary by treatment group of the number and percentage of participants with at least 1 AE, a drug-related AE, a serious AE, a serious drug-related AE, a Grade 3-5 AE, a drug-related Grade 3-5 AE, a discontinuation from study intervention due to an AE, and an AE resulting in death. Point estimates and 95% CIs for the differences between treatment groups in the percentages of participants with the event will be provided based on the criteria described below.

Point estimates and 95% CIs for the difference between treatment groups in the percentage of participants with specific AEs will be provided for AEs that occur in at least 10% of participants in any treatment group. The threshold of at least 10% of participants was chosen because the population enrolled in this study usually experiences various AEs of similar types regardless of treatment; events reported less frequently than 10% of participants would obscure the assessment of the overall safety profile and add little to the interpretation of potentially meaningful treatment differences. In addition, difference in the percentage of participants with specific Grade 3 to 5 AEs ($\geq 5\%$ of participants in 1 of the treatment groups) and SAEs ($\geq 5\%$ of participants in 1 of the treatment groups) will also be summarized by point estimates and 95% CIs.

CIs for between-treatment group differences will be provided using the Miettinen and Nurminen method [Miettinen, O. and Nurminen, M. 1985]. Because many 95% CIs may be provided without adjustment for multiplicity, the CIs should be regarded as a helpful descriptive measure to be used in safety review, not as a formal method for assessing the statistical significance of the between-group differences.

Table 9 summarizes the analysis strategy for safety endpoints in this study.

Table 9 Analysis Strategy for Safety Parameters

Analysis Part	Safety Endpoint	Descriptive Statistics	95% between-group CI (Graphical display)
Overall Safety Assessment	Specific AEs (incidence $\geq 10\%$ of participants in one of the treatment groups)	X	X
	Specific Grade 3-5 AE (incidence $\geq 5\%$ of participants in one of the treatment groups)	X	X
	Specific serious AE (incidence $\geq 5\%$ of participants in one of the treatment groups)	X	X
	Any AE	X	
	Any Grade 3-5 AE	X	
	Any serious AE	X	
	Any drug-related AE	X	
	Any serious and drug-related AE	X	
	Any Grade 3-5 and drug-related AE	X	

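### Elective unblinding after verified recurrence (Section 4.1) lacks the emergency route's step of first recording AE grade and causality, so some drug-related judgements may be made or changed with the arm known

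*Combined protocol and SAP*

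**What the plan says.** The protocol has two routes to the code.

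- **Elective (4.1).** "Participants may be unblinded after BICR-verified disease recurrence at the investigator discretion upon Sponsor consultation", and "only if this information is required to guide future treatment decisions". On documentation, "the circumstances around the unblinding (eg, date and reason) must be documented promptly". On recipients, "Only the principal investigator or delegate and the respective subject's code should be unblinded"; Sponsor staff who run the study stay blinded. No AE entry is required first.
- **Emergency (8.1.10).** Before contacting the call center, the investigator "should make reasonable attempts to enter the toxicity grade of the AEs observed, the relation to study intervention, the reason thereof" in the chart, unless that would delay the unblinding. Section 6.8 reserves the call center for emergencies, so this step does not clearly carry over to 4.1.

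Recurrence ends study intervention (7.1). Section 8.4.1 collects AEs for 30 days after cessation. Serious events are collected "from the time of intervention allocation/randomization through 90 days following cessation of study intervention", shortened to 30 days if new anticancer therapy starts. Under 10.3.5 an investigator who is a qualified physician assigns causality and may later change that opinion.

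Section 9.6.2.1 summarizes by arm, among others, "a serious AE, a serious drug-related AE, a Grade 3-5 AE, a drug-related Grade 3-5 AE". The safety population (9.5.2) and the methods in 9.6.2 make no distinction by blinding status, and 9.6.2 does not refer this matter to the supplemental SAP.

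**The concern.** Relatedness is a judgement, and 8.1.10 itself recognizes that it is best recorded before the arm is known. The elective route is not urgent and already pauses for Sponsor consultation, so the step would be easiest to apply there, yet it is absent. The person who receives the code can be the person who assigns or revises causality.

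At stake is the between-arm reading of the drug-related AE summaries. An assessor who knows the arm may attribute events more readily to pembrolizumab and less readily to placebo. Eligibility for the elective route depends on recurrence, so if the drug works more placebo participants become eligible and the exposure need not balance between arms.

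**Working it through.** **Which judgements are exposed.** Comparing the two routes and following the AE process gives three groups:

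1. AEs that began before the code-break but have no causality entry yet. The 8.1.10 step would protect these; 4.1 has no equivalent.
2. AEs judged blind and changed afterwards, which 10.3.5 permits. No analysis uses the last blinded judgement.
3. AEs that begin after the code-break but inside the 30-day window (SAEs up to 90 days). No prior entry can protect these; only a flag in the analysis can.

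**How many participants could be involved.** The plan states no figure for this, so there is none to reproduce. Inputs:

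- control median RFS 33.8 months and 950 participants randomized 1:1, hence 475 per arm (9.9.1);
- 17 doses every 3 weeks (4.3.1), so the last dose falls at about Week 48 without delays, which is 48 × 7 / 30.4375 = 11.04 months;
- exponential RFS with a constant HR and no dropout. The public text does not show the target HR, so I assume 0.7 to 0.8 and show 0.6 as well.

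The proportion with an RFS event by month t is 1 − exp(−ln 2 × HR × t / 33.8). At t = 12:

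- placebo: 1 − exp(−0.2461) = 21.8%, × 475 = 104;
- HR 0.8: 1 − exp(−0.1969) = 17.9%, × 475 = 85;
- HR 0.7: 1 − exp(−0.1723) = 15.8%, × 475 = 75;
- HR 0.6: 13.7%, × 475 = 65.

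Around the end of treatment:

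| Time | Placebo | HR 0.8 | HR 0.7 |
|---|---|---|---|
| Week 48 | 96 (20.3%) | 79 (16.6%) | 70 (14.7%) |
| Week 48 + 30 days | 104 (21.9%) | 85 (17.9%) | 75 (15.9%) |
| Week 48 + 90 days | 119 (25.0%) | 97 (20.5%) | 86 (18.2%) |

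The 12-month count therefore matches the count to the end of the 30-day window. If the same share u of these participants is unblinded in each arm, the numbers are 104u against 75u to 85u. The gap is 19u to 29u, at most 4.0% to 6.1% of an arm (19/475 and 29/475).

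The counts are ceilings. They include deaths, not every recurrence leads to an elective code-break, and the documents give no value for u.

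**The case against.** The strongest reply has four parts.

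- **The elective route is restricted.** It needs Sponsor consultation and a treatment decision that depends on the answer, and it keeps Sponsor staff blinded, which the emergency route need not. This stands and limits frequency. It does not protect a judgement made after the code is known.
- **Much is already recorded blind.** Section 10.3.5 asks for AE information at each examination and for causality before the first SAE transmission, and 10.1.9 requires traceable source changes. This stands in part: it shrinks the first group above and leaves the other two.
- **The affected tables are descriptive.** Table 9 gives the drug-related rows no between-group interval. This stands and limits the consequence.
- **The 90-day window rarely applies in full.** The code is broken to choose the next treatment, and starting that treatment cuts the SAE window to 30 days. This stands; the issue is mainly a 30-day one.

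A reader might go further and infer that all later questionnaires are answered with the arm known, since "PROs will be collected Q12W from the EOT Visit during the remainder of Year 1" after early discontinuation and collection runs to Week 252. The documents do not support that. Participants complete the PROs, and 4.1 names only the principal investigator or delegate as recipient, although its opening words leave unclear whether the participant is told. After extrahepatic recurrence participants move to Survival Follow-up (8.11.2.3), where the SoA shows no PROs. Section 9.6.3 leaves PRO analysis detail to a supplemental SAP that is not among the documents. The modeled 69.5% of placebo participants (330 of 475) with an RFS event by Week 252 therefore does not measure PRO exposure. Excluding PRO data after unblinding would also selectively remove post-recurrence assessments, more of them on placebo if the drug works.

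**Conclusion.** The point holds as a modest, inexpensive gap. The elective route omits a safeguard that the protocol applies in emergencies, and the 9.6.2 summaries cannot separate causality judged or revised after the code-break. The ceiling is about 104 of 475 placebo participants against 75 to 85 of 475 on pembrolizumab by 12 months. It rests on exponential RFS, the plan's 33.8-month control median, an assumed HR of 0.7 to 0.8 and full-length treatment. The actual number is unknown and could be much smaller, and the size of any attribution bias cannot be estimated from the documents.

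The primary endpoints are outside the point. BICR has already verified the recurrence before the elective route opens, and OS counts death from any cause. No sample-size or power figure changes.

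**What to change.** - **4.1:** before an elective code-break, require grade and causality of all AEs to date to be recorded, and the EOT PROs completed if due. State whether the participant is told the assignment.
- **eCRF:** capture the unblinding date, which 4.1 already requires to be documented.
- **9.6.2:** flag AEs whose causality was first assessed or changed after that date. Add one supportive drug-related AE summary that uses the last blinded causality, or omits AEs first assessed after unblinding.

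Access to unblinding for treatment decisions stays as it is. The cost is a short site task before a non-urgent code-break, one data field and one extra table. The supportive table may drop events unequally by arm, so it should supplement the main summary and not replace it. The entry and the date need to be captured prospectively, because a blinded judgement cannot be recreated afterwards.

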4.2 Scientific Rationale for Study Design

This Phase 3 study is designed to evaluate the efficacy and safety of pembrolizumab as adjuvant treatment in adult patients with HCC and complete radiological response after surgical resection or complete radiological response after local ablation. Treatment will be double-blinded. At the time of the study start, there are no anti-PD-1 agents approved for first-line HCC, underscoring the high unmet need for treatment of this disease, and the rationale for not allowing crossover. There is no established standard of care in the HCC adjuvant setting. Rationale for the use of a placebo as a comparator is described in Section 4.2.2. One year of adjuvant treatment is consistent with other studies evaluating pembrolizumab in the adjuvant setting in different tumor types, including melanoma, NSCLC, and RCC.

The study will be considered a success if superiority in RFS is established at either an interim analysis or the final analysis under multiplicity control as detailed in Section 9.8. The OS hypothesis will be tested only if RFS null hypothesis is rejected.

4.2.1 Rationale for Endpoints

4.2.1.1 Efficacy Endpoints

This study will have 2 primary endpoints: RFS and OS.

RFS will be based on disease recurrence (local, regional, or distant) as assessed by BICR. RFS is an acceptable measure of clinical benefit for a late-stage study that demonstrates superiority of a new antineoplastic therapy, especially if the magnitude of the effect is large and the therapy has an acceptable risk-benefit profile.

RFS has been used as the primary outcome measure in many Phase 3 studies assessing anti-PD-1 therapy in the setting of Stage III adjuvant melanoma, including S1404/KN053, EORTC1325/KN054, CheckMate 238, and COMBI-AD [Eggermont, A. M. M., et al 2018] [Weber, J., et al 2017] [Long, G. V., et al 2017]. RFS has also showed to be a valid surrogate endpoint to OS for adjuvant randomized studies assessing checkpoint inhibitors in high risk melanoma after surgical resection [Suciu, S., et al 2018].

Expedited verification of absence of radiologic evidence of disease will be performed by BICR at Screening and will be used to determine participant eligibility. Disease recurrence will be documented by investigator radiographically (with site radiologist) and will be verified by BICR. Disease recurrence can also be confirmed by pathology if required per the site's standard of care.

BICR has been advocated to control bias in randomized clinical trials that might result from errors in recurrence assessments. Bias may be introduced by the potentially subjective

components of imaging endpoint assessment. While important efforts both to minimize subjectivity and to improve consistency of radiologic endpoint assessment have been made [Therasse, P., et al 2000] [Miller, A. B., et al 1981], endpoint evaluation still depends to some extent on the individual reviewing the image and the time point at which s/he reviews it. BICR is one strategy to reduce the potential for this bias.

OS (the time from randomization to death due to any cause) after administration of pembrolizumab versus placebo will also be a primary endpoint in this study. This endpoint is precise and easy to measure, documented by the date of death. Bias is not a factor in OS measurement. Survival improvement should be analyzed as a risk-benefit analysis to assess clinical benefit [US Department of Health and Human Services and Food and Drug Administration 2005].

Overall survival (OS) has been recognized as the gold standard for the demonstration of superiority of a new antineoplastic therapy in randomized clinical studies. Overall survival is also considered the gold standard primary endpoint for studies of adjuvant treatments for cancer. However, OS can be extensively influenced by the effects of the subsequent oncologic therapies for the treatment of HCC. Thus, both RFS and OS are included as primary endpoints. The study will be considered a success if superiority in RFS is established.

CCI

4.2.1.2 Safety Endpoints

Safety is a secondary endpoint in this study.

Safety parameters commonly used for evaluating investigational systemic anticancer treatments are included as safety endpoints including, but not limited to, the incidence of, causality, and outcome of adverse events (AEs)/serious adverse events (SAEs); and changes in vital signs and laboratory values. AEs will be assessed as defined by CTCAE, Version 4.0.

4.2.1.3 Patient-reported Outcomes

Symptomatic improvement is considered a clinical benefit and accepted by health authorities as additional evidence of the risk-benefit profile of any new study intervention. In this study, HRQoL and disease-related symptoms will be investigated via the following assessment tools: [EORTC QLQ-C30, HCC-specific] questionnaires. Health utilities will be evaluated using the EQ-5D-5L PRO instrument. These measures are not pure efficacy or safety endpoints because they are affected by both disease progression and treatment tolerability.

